## **1. STATEMENT OF HYPOTHESIS AND OBJECTIVES:**

Surgical procedures are an essential piece of a dermatologist's practice. In fact, it has been reported that dermatologists perform over 25 million minor surgical procedures annually. A major focus of these procedures is to restore the integrity of the skin while minimizing scarring and potential complications. With dermatologic surgeries being so numerous, there is much discussion about how to optimize post-surgical wound care while decreasing potential barriers to healing. Recent advances in wound therapy have resulted in the development of advanced wound care therapies, such as collagen-based dressings, for use as adjunctive therapies to combat the molecular defects present in wounds.

We have designed a pilot study investigating the efficacy of Nuvagen™ (collagen powder) in treating skin punch biopsy wounds. The objectives of the study are as follows:

Primary objective:

1. To evaluate the effect of Nuvagen™ (collagen powder) on complete wound healing using punch biopsy sites as an acute full-thickness human wound model based on clinical wound closure.
2. To evaluate the effect of Nuvagen™ (collagen powder) on complete wound healing using punch biopsy sites as an acute full-thickness human wound model based on histology of wound site at 4 weeks following injury.

## **2. BACKGROUND, SIGNIFICANCE, AND RATIONALE**

Wound healing is complex process which requires the restoration of hemostasis, inflammation, proliferation, and remodeling, all of which work in concert to repair the damaged skin barrier in acute wounds. Recent advances in wound therapy have resulted in the development of advanced wound care therapies, such as collagen-based dressings, for use as adjunctive therapies to combat the molecular defects present in wounds.

Collagen is a naturally occurring protein that comprises three-quarters of the weight of human skin. Fibroblasts synthesize collagen molecules, which are composed of three polypeptide chains that together form a triple-helical structure, allowing covalent cross-linking and formation of larger fibrils and fibers. Collagen's unique structure makes it an essential component of the extracellular matrix (ECM), providing remarkable tensile strength and structural support to skin and other connective tissues. During normal wound healing, collagen acts as a scaffold for cellular ingrowth and organized collagen deposition. In addition, proteases that degrade native collagen release polypeptide fragments that act as chemotactic molecules to recruit inflammatory mediators, promote keratinocyte migration, and stimulate the proliferation of fibroblasts and subsequent collagen deposition.

Powdered or fractionated collagen products are developed through a proprietary process that involves the breakdown of natural collagen into smaller components. These collagen particles exhibit minimal cross-linking and are hypothesized to quickly replace degraded collagen fragments by bypassing enzymatic breakdown within the wound environment. Furthermore,

powdered collagen can act as a signaling molecule directly upon application, recruiting inflammatory cells and fibroblasts and supporting keratinocyte migration and ECM production.

Additionally, collagen powders have the potential to satisfy many requirements of an ideal adjunctive wound therapy. Collagen is biodegradable, non-toxic, and naturally biocompatible with low antigenicity. Collagen itself promotes thrombosis and hemostasis while having hydrophilic properties useful for absorbing fluid in exuding wounds and maintaining moisture balance. Collagen is also a poor culture medium and can be left in wounds without risk of enhancing bacterial growth. Lastly, collagen powders are easy to apply and are indicated for use in most wound types, including infected wounds.

We have designed a pilot study to investigate the effect and potential utility of topical Nuvagen™ (collagen powder) on the rate and quality of wound healing in healthy volunteers using the punch biopsy method. After inducing an acute full-thickness wound, the rate of complete healing of a wound treated with topical Nuvagen™ (collagen powder) will be compared to the rate of complete healing of a wound treated with primary closure with sutures, the current gold standard. Qualification and semi-quantification of histologic and immunohistochemical markers will be used to assess the maturity and structural stability of the wound bed. Positive findings would suggest that Nuvagen™ (collagen powder) may be capable of stimulating the healing of acute wounds in a similar or even superior manner to primary closure, suggesting collagen powder may be used in place of sutures, and encouraging further studies to characterize its therapeutic potential in dermatologic surgery.

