### **3. RESEARCH DESIGN AND METHODS**

#### **3.1 Overview of Design**

All participants will be patients that have been screened at the Department of Dermatology at the George Washington Medical Faculty Associates. Individuals taking part in the study will meet all of the inclusion criteria and none of the exclusion criteria (see Section 3.2). After completing the screening phase, subjects will receive 2 punch biopsy wounds on the thighs of each leg in their first study visit. Prior to dressing the wounds, 1 wound will be treated with primary closure, while the other will be treated with Nuvagen™ (collagen powder). Each wound will continue to be treated with the treatment designated in visit 1 (primary closure or collagen powder) for the duration of the 12-week study. After visit 1, patients will be provided with instructions and supply for daily self-administration of Nuvagen™ (collagen powder) for the wound designated for collagen powder treatment. Subjects will return weekly for 2 weeks, for suture removal if needed, photographs, wound measuring, assessment of healing, assessment of adverse events, and determination for need of further treatment with Nuvagen™ (collagen powder). Subjects will then return at week 4 for 2 additional punch biopsies at the same sites wounded at the first visit, and will be provided with similar treatment instructions as they were provided in week 1. Patients will return in 2 weeks (visit 5) for suture removal, photographs, wound measuring, assessment of healing, assessment of adverse events, and determination for need of further treatment with Nuvagen™ (collagen powder). The last study visit will be a 6 weeks after visit 5,

during which wounds will be measured and assessed for healing, while subjects will be photographed and assessed for adverse events.

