### 3.4 Treatment Phase

On the first visit, eligibility criteria will be confirmed. Investigators will select 1 area on each anterior, proximal thigh of each volunteer where one 4 mm punch biopsies will be performed. The 2 areas will be cleansed using an alcohol swab, and anesthetized using 1 mL of 2% lidocaine with epinephrine. An Integra Miltex 4.0 mm Standard Biopsy Punch instrument will be used to create 2 full-thickness wounds, one on each thigh on each leg. Hemostasis will be obtained using Aluminum Chloride 20%, application of pressure, and gauze. Each wound will be photographed with a measurement instrument and then cleaned with normal saline prior to treatment. One wound will be selected for treatment with collagen, while the contralateral wound will undergo primary closure with sutures (1-2 epidermal sutures, 4-0 Prolene™ Polypropylene Sutures, Ethicon, Somerville, NJ).

The wound selected for collagen treatment will receive 1 gram of topical Nuvagen™ (collagen powder) directly on the wound with pressure applied using a dry gauze and forceps. Once hemostasis has occurred between 1 and 5 minutes later, the wound will be covered with a sterile dressing. The other wound will undergo primary closure. Both punch biopsy sites will be covered with a non-adherent dressing and a waterproof film dressing.

The patient will be provided with a 2-week supply of Nuvagen™ (collagen powder) in 1-gram containers and dressings along with instructions. Instructions will detail the following procedure: 1) Irrigate the wound with tap water or saline solution, 2) Dry the wound with a dry gauze pad pat using gentle pressure, 3) Apply 1 gram of Nuvagen™ (collagen powder) to the wound, and 4) Apply a sterile dressing which covers the entire wound. Assistance from a caregiver will be permitted in any instance in which this procedure is difficult for the patient to carry out for him or herself. This procedure is to be repeated daily for 2 weeks. On days of study visits, patients will be instructed to bring the day's 1 gram of Nuvagen™ (collagen powder) to the clinic for study coordinators to apply the corresponding day's collagen treatment.

One week after wounding, the patient will return for visit 2. Patients will perform the Patient Overall Assessment Score, wounds will be measured, photographs will be taken, and inquiry will be made about any possible adverse events. The patient's wound treated with collagen will then be treated and dressed in the office.

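### The pilot compares two wound-care strategies, so it cannot isolate an effect of collagen, and 8 pairs with no visible difference would not show similarity to sutures

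*Combined protocol and SAP*

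**What the plan says.** **Objectives.** Section 1 opens with "We have designed a pilot study investigating the efficacy of" the collagen powder. The first primary objective concerns the product's effect "on complete wound healing using punch biopsy sites as an acute full-thickness human wound model based on clinical wound closure"; the second concerns the same effect judged on histology at 4 weeks. Neither names a comparator.

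**Comparison and interpretation.** Section 2 names the comparator: the rate of complete healing with collagen "will be compared to the rate of complete healing of a wound treated with primary closure with sutures, the current gold standard". Positive findings would suggest that collagen "may be capable of stimulating the healing of acute wounds in a similar or even superior manner to primary closure". The same sentence then draws a practical inference, "suggesting collagen powder may be used in place of sutures", before it looks ahead to further studies.

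**Design.** Section 3.1: "1 wound will be treated with primary closure, while the other will be treated with" the powder. Section 3.4: "One wound will be selected for treatment with collagen, while the contralateral wound will undergo primary closure with sutures". For the collagen wound, Section 3.4 sets out home irrigation, drying, application and re-dressing: "This procedure is to be repeated daily for 2 weeks". The investigator may extend collagen treatment by a further 2 weeks. Both sites are dressed at visit 1; later home care of the sutured wound is not described. Both sites are biopsied again at week 4 and treated as before.

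**Analysis.** Section 3.2 sets 8 patients. Section 4.3 plans descriptive statistics only, says a test would be unlikely to have power, and looks to larger studies. Section 3.6 gives small sample size as the limitation. Section 4.2 (Wound specific variables) measures the uncovered wound area on photographs.

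**The concern.** There are two separate problems.

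*Attribution.* To speak of the effect of collagen, or of collagen stimulating healing, is to say what collagen adds. That requires a wound that differs from the collagen wound in collagen only, and the design has none.

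*Similarity.* Section 2 allows a favourable reading if collagen does about as well as sutures. No margin or interval accompanies the word *similar*. The plan warns that a real difference would probably not be detected; it does not add the corollary that failing to see one is weak evidence of likeness.

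If closure looks alike on both thighs, the result could be carried into later studies as evidence that collagen stimulates healing and can replace sutures. The same result would fit collagen adding nothing to a wound left unsutured, and it would fit a sizeable closure deficit against sutures.

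**Working it through.** **Step 1: what differs between the two wounds (Sections 3.1 and 3.4).**

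| Feature | Wound A | Wound B |
|---|---|---|
| Collagen powder | yes | no |
| Sutures | no | yes |
| Written daily home routine | yes | not stated |
| Optional 2-week extension | yes | not applicable |

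The first two rows change together in every pair, and the described care differs as well. No wound is unsutured without collagen, and none is sutured with collagen. A difference, or a lack of one, therefore belongs to the whole strategy. This does not depend on sample size. Uncovered area at weeks 1 and 2 is especially hard to attribute, because suturing itself brings the wound edges together.

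**Step 2: how the thigh is chosen.** Section 3.4 says one wound is selected for collagen and describes no method. Any bias from that choice lies outside the intervals below.

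**Step 3: what 8 pairs can say about similarity.** The plan gives no closure rate, margin, alpha or power, so it has no figure of its own to reproduce. The only input it supplies is n = 8 (Section 3.2). The rest is assumption: a yes/no closure endpoint and the Tango paired score 95% interval for collagen minus suture.

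With no discordant pair, the score equation reduces to nδ/(1 − δ) = z², so the limits are ± z²/(n + z²), with z² = 1.96² ≈ 3.8415:

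- n = 8: 3.8415/11.8415 = 0.324, or ±32 points
- n = 7: 3.8415/10.8415 = 0.354, or ±35 points
- n = 6: 3.8415/9.8415 = 0.390, or ±39 points

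The smaller n matter because Section 3.5 mentions replacement only for withdrawal before treatment starts. If only the sutured wound closes in 1 of 8 patients, the interval is -47 to +24 points (numerical solution).

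**Step 4: related checks.**

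- If 8 of 8 collagen wounds close, the exact 95% lower limit for the closure proportion is 0.025^(1/8) = 0.631, or 63%.
- A true closure proportion of 80% gives 8 of 8 with probability 0.8⁸ = 0.168; a true 90% gives it with probability 0.9⁸ = 0.430.
- For continuous measures, the paired-t 95% half-width with 8 pairs is 2.365/√8 = 0.84 SD of the within-patient difference.
- If 6 of 8 patients prefer collagen, the exact 95% interval is 35% to 97%.

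**Step 5: does re-wounding help?** It gives up to 16 pair-episodes, but from the same 8 patients and at previously wounded sites. They are not 16 independent pairs. Week-4 histology has at most 8 pairs.

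**The case against.** The strongest reply is that this is a modest pilot that already says so. The Section 2 sentence is conditional throughout and ends in further research. Section 4.3 confines the analysis to description, and Section 3.6 admits the small sample. A reader might infer that the plan makes an equivalence or confirmatory claim. The documents do not support that: no test, margin or decision rule is planned, and positive findings are never defined as seeing no difference. That reading is possible because the word *similar* is left open.

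A reader might also infer that sutures are the wrong comparator or that the comparison is invalid. That does not follow either. Section 2 chooses the comparator openly, and whether collagen could be used in place of sutures is a strategy question that this contrast addresses in principle, limited by size and by the undescribed choice of thigh. Nor is the sutured wound shown to be neglected: both sites are dressed at visit 1, and only its later home care is unstated in the supplied text.

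Finally, the 32-point figure depends on the endpoint and interval chosen here. It is an illustration, not an expected deficit.

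What remains is narrower. Hedging about power does not disclose the missing collagen-free unsutured wound, Section 1 still words the objectives as an effect of the product, and a descriptive analysis does not rule out intervals.

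**Conclusion.** The concern holds in a limited form. The pilot can describe collagen without sutures next to primary closure within the same patient. It cannot isolate an effect of collagen, and this follows from the design alone. Nor could it support similarity to sutures: with a yes/no closure endpoint, 8 complete pairs and no discordant pair, differences of up to 32 points in either direction remain compatible with the data (35 with 7 pairs, 39 with 6). Those sizes rest on assumptions that the documents neither state nor contradict.

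The missing closure criterion adds to the problem: Section 2 speaks of a rate of complete healing without saying whether this is a proportion or a speed, or when a wound counts as closed. The correction should be made, but the fault is a mismatch between wording and design, not a reason to stop or redesign the pilot.

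**What to change.** 1. **Sections 1 and 2.** Word the objectives and the positive-findings sentence as a within-patient description of collagen without sutures next to primary closure. State that the pilot will not be used to conclude similarity, superiority or a collagen-specific effect.
2. **Section 3.6.** Add two limitations: there is no unsutured collagen-free wound, and no method is described for choosing which thigh receives collagen. Say that the second is a possible bias that intervals do not cover.
3. **Section 4.3, closure.** Define closure as zero uncovered area on the week-4 photograph taken before re-biopsy (Section 4.2, Wound specific variables, and Table 1). Report the paired 2×2 table with a Tango 95% score interval and the number of pairs observed. Because a week-4 yes/no result does not show speed, also list uncovered area at weeks 1, 2 and 4 by patient and wound.
4. **Section 4.3, second round.** List weeks 6 and 12 separately. Do not pool them with the first round as independent pairs.
5. **Section 4.3, other measures.** For the histology and stain measures, list within-patient differences (collagen minus suture) with the mean and a paired-t 95% interval; if all differences are zero, give the listing only, because the interval collapses to zero width. Report preference as a proportion with an exact interval.

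The cost is rewording and a few lines of analysis code. The photographs and measurements are already planned, so no new data are needed and treatment is unchanged. The downside is that the pilot's claim becomes less favourable.

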### **3. RESEARCH DESIGN AND METHODS**

#### **3.1 Overview of Design**

All participants will be patients that have been screened at the Department of Dermatology at the George Washington Medical Faculty Associates. Individuals taking part in the study will meet all of the inclusion criteria and none of the exclusion criteria (see Section 3.2). After completing the screening phase, subjects will receive 2 punch biopsy wounds on the thighs of each leg in their first study visit. Prior to dressing the wounds, 1 wound will be treated with primary closure, while the other will be treated with Nuvagen™ (collagen powder). Each wound will continue to be treated with the treatment designated in visit 1 (primary closure or collagen powder) for the duration of the 12-week study. After visit 1, patients will be provided with instructions and supply for daily self-administration of Nuvagen™ (collagen powder) for the wound designated for collagen powder treatment. Subjects will return weekly for 2 weeks, for suture removal if needed, photographs, wound measuring, assessment of healing, assessment of adverse events, and determination for need of further treatment with Nuvagen™ (collagen powder). Subjects will then return at week 4 for 2 additional punch biopsies at the same sites wounded at the first visit, and will be provided with similar treatment instructions as they were provided in week 1. Patients will return in 2 weeks (visit 5) for suture removal, photographs, wound measuring, assessment of healing, assessment of adverse events, and determination for need of further treatment with Nuvagen™ (collagen powder). The last study visit will be a 6 weeks after visit 5,

during which wounds will be measured and assessed for healing, while subjects will be photographed and assessed for adverse events.

## **Study Population**

### **3.2 Sample Size, Inclusion and Exclusion criteria**

We will enroll a total of 8 patients for this study. The inclusion and exclusion criteria for the study are as follows:

#### **Inclusion criteria:**

- Outpatient, male or female subjects of any race, 18-75 years of age
- Able to understand the requirements of the study and sign Informed Consent/HIPAA Authorization forms
- Patients willing to refrain from using topical medications to punch biopsy sites
- Patients who are willing to follow protocol instructions and return for follow-up visits
- Patients that are able to give signed informed consent for the study

#### **Exclusion:**

- Patients less than 18 years and greater than 75 years of age
- Patients that have any medical or skin condition that could impair wound healing
- Patients that have used systemic medications that suppress the immune system within 5 half-lives (if known), or 2 months of enrollment (i.e. corticosteroids)
- Patients that have applied topical steroids to the thigh(s) in the 2 weeks prior to enrollment
- Patients that are currently participating in an investigational study of a drug or device or have participated within 4 weeks of enrollment
- Patients that in the opinion of the investigator demonstrate evidence of unwillingness or inability to follow instructions or to complete the study
- Patients currently using systemic antimicrobials
- Patients with a history of diabetes mellitus
- Patients with a history of bleeding disorders or concomitant treatment with aspirin or anticoagulants (including heparin, low molecular weight heparin, warfarin, fondaparinux, or rivaroxaban)
- Patients with a history of keloids or hypertrophic scars
- Patients with other conditions considered by the investigator to be reasons for disqualification that may jeopardize subject safety or interfere with the objectives of the trial (e.g., acute illness or exacerbation of chronic illness)
- Patients with a known allergy or sensitivity to any component of the test medication (including bovine and/or collagen products) or local anesthetic agent used
- Current or previous users of tobacco products
- Recent alcohol or drug abuse is evident

- Pregnant females or nursing mothers. Eligible women of reproductive age will be required to have a negative urine pregnancy test at screening. They will also be required to be on at least 1 reliable form of effective birth control [examples: *barrier method (condoms, diaphragm), oral, injectable, implant birth control or abstinence*] during the course of this study and 30 days following the last treatment period.

### 3.3 Screening Phase

Prior to wounding and treatment, potential participants will be evaluated for study eligibility. All inclusion and exclusion criteria must be met prior to study entry and enrollment.

The patient's first visit will comprise both screening and wounding. During the screening phase, after obtaining signed informed consent, subject's personal data will be recorded. Data will include age, gender, medical and medication history and skin type. The physical examination will be performed and vital signs will be obtained. If the subject qualifies, visit 1 procedures will follow in the same visit.

### 3.4 Treatment Phase

On the first visit, eligibility criteria will be confirmed. Investigators will select 1 area on each anterior, proximal thigh of each volunteer where one 4 mm punch biopsies will be performed. The 2 areas will be cleansed using an alcohol swab, and anesthetized using 1 mL of 2% lidocaine with epinephrine. An Integra Miltex 4.0 mm Standard Biopsy Punch instrument will be used to create 2 full-thickness wounds, one on each thigh on each leg. Hemostasis will be obtained using Aluminum Chloride 20%, application of pressure, and gauze. Each wound will be photographed with a measurement instrument and then cleaned with normal saline prior to treatment. One wound will be selected for treatment with collagen, while the contralateral wound will undergo primary closure with sutures (1-2 epidermal sutures, 4-0 Prolene™ Polypropylene Sutures, Ethicon, Somerville, NJ).

The wound selected for collagen treatment will receive 1 gram of topical Nuvagen™ (collagen powder) directly on the wound with pressure applied using a dry gauze and forceps. Once hemostasis has occurred between 1 and 5 minutes later, the wound will be covered with a sterile dressing. The other wound will undergo primary closure. Both punch biopsy sites will be covered with a non-adherent dressing and a waterproof film dressing.

The patient will be provided with a 2-week supply of Nuvagen™ (collagen powder) in 1-gram containers and dressings along with instructions. Instructions will detail the following procedure: 1) Irrigate the wound with tap water or saline solution, 2) Dry the wound with a dry gauze pad pat using gentle pressure, 3) Apply 1 gram of Nuvagen™ (collagen powder) to the wound, and 4) Apply a sterile dressing which covers the entire wound. Assistance from a caregiver will be permitted in any instance in which this procedure is difficult for the patient to carry out for him or herself. This procedure is to be repeated daily for 2 weeks. On days of study visits, patients will be instructed to bring the day's 1 gram of Nuvagen™ (collagen powder) to the clinic for study coordinators to apply the corresponding day's collagen treatment.

One week after wounding, the patient will return for visit 2. Patients will perform the Patient Overall Assessment Score, wounds will be measured, photographs will be taken, and inquiry will be made about any possible adverse events. The patient's wound treated with collagen will then be treated and dressed in the office.

One week after visit 2, the patient will return for visit 3. Sutures will be removed, and the wound treated with collagen will be evaluated for further collagen treatment. The principal investigator will determine if another 2 weeks of Nuvagen™ (collagen powder) treatment will be warranted. If further collagen treatment is advised, the patient will be provided with another 2-week supply of Nuvagen™ (collagen powder) and dressings. Patients will perform the Patient Overall Assessment Score, wounds will be measured, photographs will be taken, and inquiry will be made about any possible adverse events. The wound treated with collagen will be treated and dressed in the office.

Two weeks after visit 3, the patient will return for visit 4. Both wound sites will be photographed and then biopsied again following the procedure from visit 1. Each wound will be treated identically (either with primary closure or with collagen powder) as it was in visit one. Patients will be provided with adequate supplies for at-home collagen treatment for 2 weeks. Patients will perform the Patient Overall Assessment Score, wounds will be measured, photographs will be taken, and inquiry will be made about any possible adverse events.

Two weeks after visit 4, the patient will return for visit 5. Sutures will be removed, and the wound treated with Nuvagen™ (collagen powder) will be evaluated for further collagen treatment. The principal investigator will determine if another 2 weeks of Nuvagen™ (collagen powder) treatment will be warranted. If further collagen treatment is advised, the patient will be provided with another 2-week supply of Nuvagen™ (collagen powder) and dressings. Patients will perform the Patient Overall Assessment Score, wounds will be measured, photographs will be taken, and inquiry will be made about any possible adverse events. The wound treated with collagen will be treated and dressed in the office.

Six weeks after visit 5, the patient will return for visit 6. Patients will perform the Patient Overall Assessment Score, wounds will be measured, photographs will be taken, and inquiry will be made about any possible adverse events.

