### **3.5 Study Completion and Withdrawal Criteria**

It is the right and duty of the Investigator to discontinue the study participation of a subject when the subject's health or well-being is threatened by continuation in the study. Such subjects should be withdrawn from the study and not continued under a modified regimen.

The following are circumstances that would result in the subject's discontinuation from the study:

- The subject experiences a serious adverse event rendering them unable to continue study participation;
- The subject is unable to physically or mentally tolerate the use of the least medication;
- An exclusion criterion becomes apparent at any time during the study, or the subject voluntarily withdraws.

In the event of premature discontinuation from the study, the Investigator should determine the primary reason for discontinuation. A subject who is withdrawn from the study prior to initiation of treatment may be replaced.

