### **3.6 Strength and Limitations of Proposed Research**

Strengths of the study include its relatively simple design and the potential for its completion within a short period of time due to the small number of participants (eight).

Limitations of this study include the inability to conduct robust statistical analysis due to its small sample size. However, the results of this project may lead to the development of larger studies that will have the statistical power to detect improvements.

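### The plan does not say how the collagen wound is chosen, so the collagen-versus-suture comparison can reflect the choice of wound rather than the treatment

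*Combined protocol and SAP*

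**What the plan says.** Each of 8 participants has one punch wound on each thigh. One wound gets collagen powder and the other is sutured. On which wound gets which, Section 3.4 says only that "One wound will be selected for treatment with collagen, while the contralateral wound will undergo primary closure with sutures". Section 3.1 likewise gives one treatment to each wound without a method.

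In Section 3.4 the investigators pick one area on each thigh, make both wounds and obtain hemostasis. Then "Each wound will be photographed with a measurement instrument and then cleaned with normal saline prior to treatment". The selection sentence comes next.

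The choice made at visit 1 lasts for the whole study. At week 4 there are "2 additional punch biopsies at the same sites wounded at the first visit", and "Each wound will be treated identically (either with primary closure or with collagen powder) as it was in visit one".

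The comparison is central to the study's purpose. Section 2 says that healing under collagen "will be compared to the rate of complete healing of a wound treated with primary closure with sutures", and that a positive finding would suggest collagen might replace sutures. Section 4.3 plans descriptive statistics only. On limitations, Section 3.6 says: "Limitations of this study include the inability to conduct robust statistical analysis due to its small sample size". It does not mention treatment assignment.

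**The concern.** Comparing two wounds in the same person removes differences between people. It does not remove differences between the two wounds or the two thighs, and those are what the choice of wound acts on. If whoever chooses can see both wounds and knows both treatments, then bleeding, wound edges or ease of access can influence the choice, knowingly or not. If one side is used by habit, treatment and side cannot be separated at all.

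The first wound episode feeds both primary objectives, clinical closure and week 4 histology. Where the choice tracks a lasting side or site difference, the second episode is affected too, because sites and treatments are reused. With descriptive analysis only, readers will carry the observed direction of the difference forward to larger studies, and a non-random choice shifts that direction. Week 0 photographs and measurements could reveal, or partly adjust for, a recorded imbalance. They cannot do so for unrecorded features or a fixed side.

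**Working it through.** **Text check.** The supplied text was read for any mention of random assignment, a side rule, a sequence, the person who chooses, or concealment.

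| Place | What it gives on assignment |
|---|---|
| Table of contents | no randomisation section |
| 3.1 | one wound to each treatment; no method |
| 3.4, visit 1 | one wound is selected; no chooser, rule or concealment |
| 3.4, visit 4 | same treatment as at visit 1 |
| 4.3 | no mention |
| Table 1 | no assignment step |

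That the choice follows sight of both wounds is inferred from the order of sentences in 3.4. The title pages were not in the supplied text.

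**Size.** The plan has no figure to reproduce: 8 is stated without a variance, effect size or power. What follows is an assumed model.

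Let D be the outcome difference between a person's two wounds with no treatment effect, with standard deviation s. Let A be the visible difference in appearance, with correlation r to D:

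D = s(rA + √(1 − r²)e), with A and e independent standard normal.

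Let p be the share of people in whom the better-looking wound gets collagen. Then:

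- bias of the mean = √(2/π) × r × (2p − 1) × s = 0.798 × r × (2p − 1) × s
- standard error with 8 pairs and no selection = s/√8 = 0.354 s

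Example: for p = 1 and r = 0.3, bias = 0.798 × 0.3 × 1 × s = 0.24 s, and 0.24/0.354 = 0.68 standard errors.

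The last column is from simulation (400,000 trials of 8 pairs, no true effect).

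| p | r | Bias (in s) | Bias (in standard errors) | Chance the mean favours collagen |
|---|---|---|---|---|
| 0.5 | any | 0 | 0 | 50% |
| 0.6 | 0.1 / 0.3 / 0.5 | 0.02 / 0.05 / 0.08 | 0.05 / 0.14 / 0.23 | 52% / 55-56% / 59% |
| 0.75 | 0.1 / 0.3 / 0.5 | 0.04 / 0.12 / 0.20 | 0.11 / 0.34 / 0.56 | 54% / 63% / 72% |
| 1 | 0.1 / 0.3 / 0.5 | 0.08 / 0.24 / 0.40 | 0.23 / 0.68 / 1.13 | 59% / 76% / 89% |

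Bias equals one standard error when r = 0.354/(0.798 × (2p − 1)). That is r = 0.44 at p = 1 and r = 0.89 at p = 0.75. At p = 0.6 it would need r = 2.2, which is impossible.

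**Closed or not closed.** Suppose exactly one of the two wounds is closed in a share d of people, and it is the better-looking one in a share q of those. The expected spurious excess of closed collagen wounds is 8 × d × (2q − 1) × (2p − 1). At p = 1:

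| d | q = 0.6 | q = 0.75 |
|---|---|---|
| 0.125 | 0.2 wounds | 0.5 wounds |
| 0.25 | 0.4 | 1 |
| 0.5 | 0.8 | 2 |

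At p = 0.75 these halve. The standard error of the same count without selection is 8 × √(d/8) = 1.0, 1.4 and 2.0 wounds for the three values of d.

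If the worse-looking wound is favoured for collagen, every sign above reverses.

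**Fixed side.** If one side is always used, the bias is the mean left-right difference in outcome. The documents do not give it, and nothing in the data could separate it from the treatment effect.

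**The case against.** The design leaves little to select on. Both wounds are made with the same 4 mm instrument in matching areas with the same anaesthetic and hemostatic agent, and people with conditions that impair healing are excluded. The plan states no preference for the better-looking wound, and an indifferent choice (p = 0.5) gives no bias from appearance. The largest figures need a near-perfect preference together with a strong link between appearance and outcome. All of this stands, and it is why the likely effect is uncertain and may be modest. It does not cover a fixed side, which needs no visible difference between wounds.

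Clinical closure is also a poor fit to a model of no true effect: one wound is sutured at once and the other is left open, a contrast that may outweigh any selection effect. That stands for early closure. It is weaker for week 4 histology and patient ratings, which lack so direct a built-in difference.

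The study is a descriptive pilot with cautious conclusions, and no test depends on assignment. This limits the harm but does not remove it, because the observed direction is the main comparative message the study will produce. Finally, assignment before wounding is not excluded by the text. If that or randomisation is intended, the protocol should say so.

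**Conclusion.** The concern holds. The supplied text gives no method of assigning treatment to wound, and staff could follow it exactly while choosing after seeing both wounds or always using one side. The omission is clear from the text; the resulting bias is not measured. Under the assumed model it runs from zero (indifferent choice) to 0.40 s, or 1.13 standard errors, when r = 0.5 and the better-looking wound always gets collagen, and it may go in either direction. It exceeds one standard error only under strong selection. A fixed side would confound side with treatment completely.

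This should be fixed before enrolment, because assignment cannot be repaired once wounds have been treated. It does not invalidate the study.

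**What to change.** Replace the selection sentence in Section 3.4 with random assignment of the left or right thigh to collagen:

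- A computer-generated list is prepared before the first participant by someone not involved in wounding or wound assessment, and kept concealed, for example in numbered sealed envelopes.
- The envelope is opened only after both areas are chosen and both wounds are made, hemostatic and photographed.
- The treated side is recorded, and kept at visit 4 as already planned.
- Section 3.5 says: "A subject who is withdrawn from the study prior to initiation of treatment may be replaced". An envelope still unopened passes to the replacement. If it was already opened, the replacement takes the next unused one, so the list needs a few spare entries.

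Random assignment makes the expected selection bias zero. Blocking is for the sponsor's statistician to decide. Without it, collagen would fall on the same side in at least 7 of 8 people with probability 2 × (8 + 1)/256 = 0.07, so a side-balanced list is a sensible refinement.

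The cost is one protocol sentence, a short list, a few envelopes and a small task for someone outside wounding and assessment. No patients, visits or procedures are added.
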